7.2. Secondary outcomes

1. Iohexol-clearance GFR at the end of the 3-year treatment period (before the washout).
2. Iohexol-clearance GFR time trajectory estimated from periodical iohexol-GFR measurements.
3. Estimated (eGFR) at 4 months estimated from serum creatinine and cystatin C and adjusted for the eGFR at baseline.
4. Estimated GFR (eGFR) time trajectory estimated from quarterly serum creatinine and cystatin C measurements using the CKD-EPI SCr and the CKD-EPI SCr-SCysC equations.^{34,35}
5. Time to doubling of baseline serum creatinine value or ESRD (eGFR ≤ 15 ml/min/1.73 m², institution of dialysis, kidney transplantation).
6. Geometric mean of two AER measurements at the end of the 2-month wash-out period following the 3-year treatment period, adjusted for the mean urinary AER at baseline. Urinary

AER will be determined in timed overnight urine collections brought by study participants to regular clinic visits, and expressed in $\mu\text{g}/\text{minute}$ and as urinary albumin/creatinine ratios.

7. Geometric mean of urinary AER during the last three months of the treatment period (Visits 15 and 16), adjusted for the mean urinary AER at baseline.
8. Time to fatal or non-fatal cardiovascular events, defined as the composite of CVD death (ICD-10 code I10 to I74.9), myocardial infarction, stroke (ischemic or hemorrhagic), coronary artery bypass grafting, or percutaneous coronary intervention.

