5.5. Discontinuation of study drug

5.5.1. Reasons for discontinuation

The study drug will be *temporarily* discontinued if a participant:

- Has clinically significant persistent changes from baseline based on laboratory safety assessment results (the response to discontinuation will be monitored to assess whether the drug can be re-instituted, see next paragraph on permanent discontinuations).
- Requires treatment with allopurinol or medications that make allopurinol contraindicated (see 5.5.2 and 9.5).
- Becomes pregnant or breastfeeding (see 5.5.2)

Whenever the reason for temporary discontinuation of the study drug ceases to exist, the study medication will be resumed with the consensus of the drug monitoring committee, according to the following procedures:

- If the study medication was discontinued because of a suspected drug reaction or the participant was off-medication for 3 months or longer, the study drug will be re-started at a dosage of 100 mg for 4 weeks, which will then be increased to the full dosage appropriate for the eGFR. (see 6.1.2)
- If the study medication was not discontinued because of a drug reaction and the participant was off-medication for less than 3 months, the study medication will be re-started, at the full dosage appropriate for the eGFR.

The study drug will be *permanently* discontinued if a participant:

- Experiences an SAE related to the study drug or an intolerable AE such as a persistent allergy or rash.
- Has clinically significant persistent changes from baseline based on laboratory safety assessment results which do not respond to temporary 2-week discontinuation of study drug and re-institution of drug at ½ of the initial dose.
- Develops end-stage renal disease (confirmed eGFR ≤ 15 ml/min/1.73 m² in the absence of acute kidney injury [AKI], institution of chronic dialysis treatment or kidney transplantation) or iGFR decreases by 50% from one measurement to the next or serum creatinine levels double over any 12 month interval in the post-randomization period. If any of these renal function changes prove to be temporary, the study medication could be resumed as described above with the consensus of the drug monitoring committee.

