5.5.2. Handling of study drug discontinuation

- Date and reason for drug discontinuation will be recorded on the relevant Case Report Form.
- All study discontinuations decided by a clinical site will have to be reviewed and approved by the Drug Monitoring Committee within 10 days from their start.
- If the study drug is discontinued due to treatment with medications that make allopurinol contraindicated (e.g. amoxicillin/ampicillin) or due to pregnancy/breastfeeding, the possibility of resuming the study drug will be evaluated by the Drug Monitoring Committee once those medications have been discontinued or pregnancy/breastfeeding has ended.

- If the study drug is temporarily discontinued and then re-instated, the end-date of the intervention will remain the same as if the study drug had not been discontinued. All visits will be carried out as scheduled while the study drug is temporarily discontinued.
- Unless a participant withdraws consent all participants that are permanently discontinued from study drug or who discontinue study medication on their own will be followed for the full study period (i.e., 164 weeks, including the washout period) and all data will be collected as scheduled.
- If a participant reaches ESRD as defined above under 5.5.1,, he/she will be permanently discontinued from the study and invited to participate in a study close-out call or visit to be held within three months from the occurrence of ESRD. Data collection at this call or visit will be limited to standard adverse event reporting. In addition, sites should continue to contact participants who have reached end-stage renal disease to determine their final status until 3 years and 2 months after randomization. Major attempts will be made to schedule an end-of-study assessment for all participants who are lost to follow-up during the course of the study.

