11.4. Secondary Efficacy Analyses

1. The effect of treatment on the iGFR at the end of the 3-year treatment period (before the washout) will be evaluated using the same analytical approach employed for the primary outcome.
2. The effect of treatment on the eGFR at 4 months after randomization will be evaluated using the same analytical approach employed for the primary outcome.
3. The iGFR and eGFR time trajectories, estimated from periodical iGFR measures and quarterly serum creatinine and cystatin C measurements using the CKD-EPI SCr and the CKD-EPI SCr-SCysC equations^{34,35}, respectively, will be analyzed using linear mixed-effects models.⁴⁰⁻⁴² The main objective of the analysis will be to construct confidence interval for the effect of the intervention over three years of observation (treatment main effect) and investigate whether the effect of the intervention changes with time (time by treatment interaction).
4. Time to serum creatinine doubling or ESRD in the two treatment groups is subject to censoring due to dropouts or reaching the end of study before the participant experiences the event. Survival time will be defined as the time from randomization to the event (the first of serum creatinine doubling from baseline or occurrence of ESRD, defined as eGFR \leq 15 ml/min/1.73 m², hemodialysis, or kidney transplant) or, for participants who did not experienced an event, to the last study visit. Data will be summarized by means of Kaplan-Meier survival curves and by providing the proportions of participants surviving without events at 1, 2, 3 years, and at the end of the wash-out period along with their 95% CIs. Given the potentially small number of events, differences between study groups will be tested by means of the log rang test or by means of simple Cox regression models including a limited number of predictors in addition to treatment group.
5. The effect of treatment on the AER at the end of the wash-out period, based on the geometric mean of two AER measured at this time point and adjusted for the geometric mean of AER at baseline (Visit 3 and 4), will be investigated in a linear regression model framework as in the case of the primary outcome.

6. The effect of treatment on the AER at the end of the treatment period, based on the geometric mean of the AER measures at visit 15 and 16 adjusted for the geometric mean of AER at baseline (Visit 3 and 4) will be investigated as in #5.

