5.2.4. Estimand for estimated GFR (eGFR) time trajectory

This is de-facto (effectiveness) estimand for eGFR trajectory with the following attributes:

A1. Target population: Individuals with T1D meeting the inclusion/exclusion criteria specified in the Study Protocol.

A2. Variable of interest (endpoint): Repeated eGFR measures at all post-randomization visits (Visit 6 through 17) as estimated from repeated serum creatinine and cystatin C measurements using the CKD-EPI SCr and the CKD-EPI SCr-SCysC equations.

A3. Strategies for different groups of IC events: The same as those used for primary estimand (see Section 5.1)

A4. Population summary to compare treatments: Population-average treatment effect on the slope of post-randomization eGFR trajectory

5.2.5. Estimand for time to doubling of serum creatinine or end-stage renal disease (ESRD)

This is de-facto (effectiveness) estimand for doubling of serum creatinine or developing ESRD with the following attributes.

A1. Target population: Individuals with T1D meeting the inclusion/exclusion criteria specified in the Study Protocol.

A2. Variable of interest (endpoint): This secondary endpoint is defined as a composite of two events: (1) doubling to serum creatinine, and (2) ESRD. Time to event is defined as time from randomization to the first event (one of the events defined above) or censoring (lost-to-follow-up, withdrawal, death, and study completion without experiencing the event).

A3. Strategies for different groups of IC events: Depending on IC event group membership (see Table 5.1) variable of interest/endpoint values, collected after IC event in

- Group A will be considered as directly interpretable. Effectively IC events in this group are ignored, which is consistent with the ITT principle.

- Groups B and C are assumed to conform a hypothetical scenario in which the variable of interest/endpoint values have a similar distribution to subjects not experiencing the IC event.

A4. Population summary to compare treatments: Hazard ratio for allopurinol versus placebo.

5.2.6. Estimand for urinary AER at the end of the two-month wash-out period (Visit 17)

This is de-facto (effectiveness) estimand for AER at V17 with the following attributes.

A1. Target population: Individuals with T1D meeting the inclusion/exclusion criteria specified in the Study Protocol.

A2. Variable of interest (endpoint): Geometric mean of two urinary AER measures obtained at Visit 17.

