We will also include eGFR at all post-randomization visits, i.e., Visit 6-17, iGFR at Visits 11, 16 and 17, AER at Visits 15, 16 and 17 expressed on logarithmic base to 10 scale. Imputation of baseline variables will be performed starting with variables having the lowest number of missing values. Variables measured longitudinally, i.e., eGFR and iGFR, will also be modeled sequentially in order determined by visit number. To preserve different response patterns in the study treatment groups (i.e., treatment group by study visit interaction) imputations will be performed separately in each group. Resulting data will consist of 25 imputed datasets. We note that the FCS method imputes data under the missing at random (MAR) assumption, e.g., the probability that the iGFR/eGFR value is missing depends on *observed* rather than *unobserved* values of the variable. Although we consider the MAR assumption to be sensible for our study, it does not apply for post-ESRD iGFR/eGFR values. To model *post-ESRD eGFR* measures as a deviation from the MAR assumption, we will impute these values using a controlled imputation technique, specifically the delta-adjustment approach (O’Kelly, Ratitch, 2014). This technique will impute post-ESRD eGFR values on average at 7 ml/min/1.73m², with a small variation around it, that is consistent with: (1) attributing to missing post-ESRD eGFR values the value representing ‘the worst case scenario’, (2) assigning a biologically acceptable value, and (3) including the ‘absorbing state’ feature of ESRD. We note that eGFR measures are taken at every visit and are used to determine time of developing ESRD. For this reason pre-ESRD eGFR values are highly predictive of post-ESRD iGFR values. In addition, we note that post-ESRD iGFR and eGFR values lie in a very narrow range and they are effectively interchangeable. For these reasons, we will impute post-ESRD iGFR values by using corresponding post-ESRD eGFR imputed values as a proxy. We note that the imputation of *eGFR* and *iGFR* values for subjects who *did not develop* ESRD and have low values to start with may lead to imputed values lower than 15 ml/min/1.73m², which is biologically implausible. For this reason, imputed values of *eGFR* and *iGFR* for subjects who *did not develop* ESRD will be truncated at 15 ml/min/1.73m². Similarly, log(AER) base 10 imputed values for these subjects will be truncated at a lower limit of detection of -0.60206 (= log₁₀(0.25)).

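### The secondary ESRD endpoint counts any eGFR of 15 or less and any dialysis, Protocol 5.5.1 requires confirmation without AKI or chronic dialysis, and the SAP body does not say which definition governs

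*Protocol*

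**What the plan says.** **Endpoint.** Protocol 7.2 item 5 is "Time to doubling of baseline serum creatinine value or ESRD". ESRD there is an eGFR of 15 or less, "institution of dialysis, kidney transplantation". Protocol 11.4 item 4 runs survival time to "the first of serum creatinine doubling from baseline or occurrence of ESRD, defined as eGFR" of 15 or less, hemodialysis or transplant. Neither place asks for confirmation, excludes AKI or limits dialysis to chronic dialysis. Appendix I of the SAP reproduces both.

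**Drug discontinuation.** Protocol 5.5.1 requires a confirmed eGFR of 15 or less "in the absence of acute kidney injury [AKI], institution of chronic dialysis treatment or kidney transplantation". It then allows for recovery: "If any of these renal function changes prove to be temporary, the study medication could be resumed".

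**Follow-up.** Protocol 5.5.2 ties study exit to that stricter definition: "If a participant reaches ESRD as defined above under 5.5.1", the participant leaves the study. Others who stop study drug are followed to week 164 unless they withdraw consent.

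**SAP body.** Section 5.2.5 defines the endpoint as a "composite of two events: (1) doubling to serum creatinine, and (2) ESRD" and says no more about what ESRD is. In Table 5.1 the Group B intercurrent event is treatment for ESRD. Section 6.5 says: "We note that eGFR measures are taken at every visit and are used to determine time of developing ESRD". Missing eGFR after ESRD is imputed at about 7, and those values stand in for iGFR. Imputed values for participants without ESRD are cut off below at 15.

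**The concern.** One current protocol uses one term with two meanings. The stricter meaning governs stopping drug and leaving the study. The looser one governs a secondary efficacy endpoint. AKI can take eGFR to 15 or below for a short time, and 5.5.1 itself recognises that such changes may reverse. Under 7.2 and 11.4 the same episode is an ESRD event at its first occurrence, and nothing later can undo it.

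Two things are at stake. First, 11.4 expects few events in this composite, so a small number of reversible episodes could be a visible share of it. Such events would tend to pull the hazard ratio towards 1 if they are unrelated to treatment. Second, in SAP 6.5 the ESRD label decides how a missing GFR is filled in: at about 7 with the label, or from the participant's other data with a floor of 15 without it. An unclear label therefore leaves a choice open in the primary analysis.

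**Working it through.** **1. The definitions side by side**

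| Element | Protocol 7.2 item 5 | Protocol 11.4 item 4 | Protocol 5.5.1 |
|---|---|---|---|
| eGFR of 15 or less | any value | any value, first occurrence | confirmed, no AKI |
| Dialysis | any | hemodialysis, duration not stated | chronic only |
| Transplant | yes | yes | yes |

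Take a participant with one visit eGFR at or below 15 during AKI and recovery by the next visit. Under 7.2 and 11.4 this is an ESRD event. Under 5.5.1 it is not ESRD, and under 5.5.2 the participant stays in follow-up. Short-term hemodialysis for AKI with recovery splits the same way.

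**2. What the SAP does with that participant**

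- Visit 17 iGFR observed: 6.5 assigns about 7 to missing post-ESRD values, and 3.2 explains the imputation by iGFR not being measured after ESRD. Nothing describes replacing an observed value.
- Visit 17 iGFR missing, Table 5.1 Group B governs: an untreated fall is not a Group B event, so the value of 7 does not apply.
- Visit 17 iGFR missing, the 5.5.1 definition governs: not ESRD, so ordinary imputation with a floor of 15.
- Visit 17 iGFR missing, a visit eGFR of 15 or less is enough: ESRD, imputed at about 7.

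The SAP body does not choose among the last three.

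**3. The plan's own figures**

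No event count, rate or power is given for the ESRD endpoint, so nothing there can be reproduced. The yardstick for the imputation is the primary design in Protocol 11.10: effect 3, residual SD 10.1, two-sided alpha 0.05, power 80%.

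n = 2 × (1.960 + 0.842)² × 10.1² / 3² = 178 per group, against 180 stated. With 15% dropout and 6% non-compliance, 180 / (0.85 × 0.94²) = 239.7, against 240 stated. The target of 3 is reproduced as the design basis, and the definitional point does not affect it.

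**4. Shift in an arm mean per affected case**

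Inputs: N = 530 (SAP section 1), so 265 per arm if the 1:1 split is exact (assumption); imputed mean 7 (SAP 6.5); G = the Visit 17 iGFR that would otherwise have been imputed (assumption, from the SAP floor of 15 up to 60).

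Shift = (G − 7) / 265

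- G = 15: 8 / 265 = 0.03
- G = 30: 23 / 265 = 0.09
- G = 60: 53 / 265 = 0.20

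Against the target of 3 this is about 1% (0.03 / 3) to 7% (0.20 / 3) per case. The documents give no rate of transient falls, so there is no basis for multiplying by a number of cases.

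**5. Dilution of the composite, illustration only**

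Assume 12 true control events, a true hazard ratio of 0.60, and f false events in each arm that would not have entered through creatinine doubling. With equal arms and few events the ratio of counts approximates the hazard ratio:

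(12 × 0.60 + f) / (12 + f)

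- f = 1: 8.2 / 13 = 0.63
- f = 4: 11.2 / 16 = 0.70

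None of these inputs comes from the documents. The calculation shows the direction of the effect, not its size.

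**The case against.** **A stopping rule and an endpoint may use different definitions.** In principle they may. But the protocol uses one term, gives no sign that the difference is deliberate, and acknowledges in 5.5.1 that the changes can reverse. The objection does not explain why acute dialysis should be an ESRD endpoint event.

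**The primary analysis.** A reader might infer that transient falls distort the primary result. The documents do not support that. Unconfirmed cases stay in follow-up, about 7 is described for missing values only, Group B is ESRD treatment, and 6.5 calls ESRD an absorbing state, which does not fit a reversible fall. The harm needs a transient fall seen at a visit, a later missing GFR, and a programmer applying the bare threshold. That is possible because the SAP leaves it open, but it is not established. The alternative value would also be imputed from the participant's own eGFRs, including the low one, which favours the lower part of the 0.03 to 0.20 range. In a blinded trial with no stated reason for imbalance, cases in the two arms would partly offset each other.

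**Creatinine doubling.** A reader might also infer that unconfirmed doubling, or the unconfirmed 40% eGFR fall in SAP 6.8.5, is the same error. It is not: 5.5.1 does not require confirmed doubling either, and the 40% fall is an added analysis with no conflicting text. There is a related limit on what the correction achieves. From the usual lower entry limit of 40, a fall to 15 is a ratio of 40 / 15 = 2.67. If creatinine moves roughly in inverse proportion to eGFR (an assumption; the documents do not print the equation), the same sample would often meet the doubling criterion too. Aligning ESRD may therefore remove fewer events from the composite than from its ESRD component. That limit stands.

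**Conclusion.** The contradiction is real and lies in current text. Followed literally, 7.2 item 5 and 11.4 item 4 turn a reversible fall or acute dialysis into an ESRD event, contrary to 5.5.1. It should be corrected for the secondary composite and for the added composite in SAP 6.8.6, which shares the ESRD component. Its size there cannot be computed, because no AKI rate or event rate is given.

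The link to the primary analysis is an open specification, not a demonstrated bias. On the one reading that triggers it, each affected participant would shift an arm mean by about 0.03 to 0.20 ml/min/1.73 m² against a target of 3. This assumes 265 per arm and an otherwise imputed value of 15 to 60. The documents support no total across participants.

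It would be inaccurate to say that the SAP nowhere gives the definition: Appendix I repeats the looser protocol wording. The definition is absent from the SAP body, where the derivations are specified.

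**What to change.** Reconcile the passages as follows.

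- Use one endpoint definition of ESRD in Protocol 7.2 and 11.4 and in SAP 5.2.5, 6.7.5 and 6.8.6: a confirmed eGFR of 15 or less not due to AKI, chronic dialysis, or transplant.
- Use the same definition to trigger the SAP 6.5 imputation, and reconcile it with Group B in Table 5.1.
- State that eGFR and iGFR values observed after the event are kept.
- State how a first qualifying eGFR at Visit 17 is handled, since no later visit is scheduled to confirm it.
- Show the unconfirmed definition as a sensitivity analysis.

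The drug-stopping rule is not affected, and no view is taken on it. Confirmation of creatinine doubling and of the 40% eGFR fall is optional. It is a design choice, would need its own last-visit rule, and is not part of this error.

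The cost is wording and derivation code. Central creatinine is already scheduled at every follow-up visit, and Protocol 8.1 already allows extra samples when a change needs confirming. The downside is slightly fewer events.

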8. STUDY PROCEDURES

8.1. Schedule of Events

The schedule of events that will take place in the proposed study is outlined in Figure 1. Visits will be frequent during the Run-In period and during the first 30 days after randomization in order to escalate the allopurinol dosage and closely monitor the occurrence of AEs. After that, participants will be seen every 3-4 months to monitor their UA levels, renal function, occurrence of AEs, and medication compliance and, if necessary, to perform interventions to improve compliance. Visit 1 will be considered as Time 0 for scheduling Visits 2-5, Visit 5 will be considered as Time 0 for scheduling Visit 6-16, Visit 16 as Time 0 for scheduling Visit 17. The study windows that define when study visits may occur are noted in Figure 1 and differ by type of visit. Visits 2, 3, and 6 will be carried out within 6 business days (before or after) from their scheduled dates; visits 11, 16, and 17 within 2 weeks before and 4 weeks after their scheduled dates; visit 4A (if necessary) within 1 week before and 3 weeks after its scheduled date, and all other visits within 2 weeks (before or after) from their schedule dates. Additional blood or urine samples may be required in between visits if clinically significant changes are observed in blood or urine measurements that need to be confirmed or otherwise monitored. iGFR measurements may be repeated for medical reasons or technical problems (see 7.1). Safety laboratory tests (CBC, serum creatinine, K^+ , ALT, and pregnancy tests in women) will be performed by local laboratories. Outcome variables (plasma iohexol, serum creatinine and cystatin C, urinary AER), HbA1c, and serum uric acid will be measured by the Central Laboratory at the University of Minnesota, directed by [name].

Figure 1. Schedule of Events

Year	1	1	1	1	1	1	1	1	1	1	2	2	2	3	3	3	3	3
Week	-12	-9	-7	-3	0	4	16	32	48	64	80	96	112	128	142	156	164	
Visit #	1	2	3	4	4a*	5	6	7	8	9	10	11	12	13	14	15	16	17
^Type of Visit: In-Person Visit Required (V); Phone Call (C); Other Visit (In-Person or Remote Visit, O)	O	V	O	V	V	C	O	O	O	O	O	V	O	O	O	O	V	V
EVENT	Screen	Run-in				RANDO 100 mg	Allopurinol or placebo										Wash-out	
		200-400 mg										EOS						
Informed Consent	x	x																
Demographics	x																	
Initial Medical Hx		x																
Interval Medical Hx and BP Control			x	x	(x)		x	x	x	x	x	x	x	x	x	x	x	x
Concomitant Meds	x	x	x	x	(x)		x	x	x	x	x	x	x	x	x	x	x	x
Blood Pressure and Measurements	x	x	(x)	x	(x)		(x)	(x)	(x)	(x)	(x)	x	(x)	(x)	(x)	(x)	x	x
ECG Report		x		x	(x)							x					x	
Physical Exam		x		(x)	(x)							x					x	
Skin Assessment				x	(x)		x	x	x	x	x	x	x	x	x	x	x	x
Eligibility	x			x	(x)	x												
Randomization						x												
Family History				x	(x)													
RAS and BP Med Log		x	x	x	(x)		x	x	x	x	x	x	x	x	x	x	x	x
IGFR Procedure				x	(x)							x					x	x
PERL Study Drug Prescription						x	x	x	x	x	x	x	x	x	x	x	x	
Study Drug Compliance							x	x	x	x	x	x	x	x	x	x	x	
CENTRAL LAB																		
Serum uric acid, serum creat, cystatin C	x		x	x	(x)		x	x	x	x	x	x	x	x	x	x	x	x
Urine ACR/AER	x		x	x	(x)				x		x						x	x
HbA1c	x			x	(x)			x	x	x	x	x	x	x	x	x	x	x
HLA B*58:01				x	(x)													
iGFR				x	(x)							x					x	x
NIDDK Repository: serum, plasma, urine				x								x					x	x
LOCAL LAB																		
Pregnancy test serum HCG	x		x	x	(x)		x	x	x	x	x	x	x	x	x	x	x	x
Pregnancy test urine dipstick		x		x	(x)							x					x	x
ALT, K, CBC, serum creatinine, urine	x		x	x	(x)		x	x	x	x	x	x	x	x	x	x	x	x
Protocol Deviation		x	x	x	(x)		x	x	x	x	x	x	x	x	x	x	x	x
Adverse Events		x	x	x	(x)	x	x	x	x	x	x	x	x	x	x	x	x	x

*If normal blood pressure control is not achieved at Visit 4, the run-in period may be extended for two more weeks after which participants will be examined as in Visit 4 (Visit 4A). In this event, the GFR measurement scheduled for Visit 4 will be conducted at Visit 4A.

^ Study visits will be generally conducted at the Study Sites or their Satellites. "In-Person Visits" (V) are required for Visit 2 and all visits requiring iohexol-GFR measurements. If a participant lives far from a study site or satellite, or travel impediments are present, other (O) visits may be conducted remotely or in-person. For any given study visit to be conducted remotely, a Phone Visit and a Remote Biospecimen Collection will be both required; a Phone Visit is performed by the study coordinator using the telephone or other media such as Skype to collect results of study procedures that do not require physical interactions (e.g., collection of medical history), and a Remote Biospecimen Collection is performed at a clinical laboratory close to where participants live.

Note: (x) indicates an optional assessment For BP and Measurements, (x) indicates an optional assessment only if the patient is NOT seen in-person.

